Newborn infants diagnosed with neonatal encephalopathy undergoing cooling therapy for neonatal encephalopathy irrespective of gender or race are eligible for this study. We aim to recruit patients both in English and Spanish.

All four of the following criteria must be met to qualify for the cooling protocol

1. Age: less than 1 day old
2. Gestational age > 35wks
3. Evidence of birth depression, either
 - a. 10 minute Apgar score less than 5
 - b. Need for cardiopulmonary resuscitation at 10 minutes of age
 - c. Blood pH < 7.0 within the first 1-hour of life
 - d. Base excess lower than -12 (i.e. base deficit more than 12) within the first hour of life
4. Evidence of encephalopathy based on clinical (neurological examination) or on aEEG/cEEG assessment.

Exclusion Criteria:

1. Major congenital or genetic abnormalities
2. Infants more than one day old
3. Known allergy/sensitivity or any hypersensitivity to components of study drug
4. Maternal illicit drug or alcohol use during pregnancy
5. If the baby had a proven (i.e. electrically confirmed seizure) prior to enrollment

5) Study Timelines

We expect to complete this study within 2 years. We have 13 patients already enrolled and our goal is 42 total (study arm n=21 and control arm n=21). We have chosen a sample size of 42 as this sample size will have an 80% chance of detecting a reduction of seizure rate by 2/3 with a p-value of 0.05.

At our institution alone we have ample experience in whole body cooling having cooled 31 patients in 2015, 28 patients in 2016, and most recently 26 patients in 2017. Patients will be asked to come for a one hour follow up outpatient clinic (MIND Institute) visit at the at 9, 18, and 27 months of age (all infants who receive cooling are asked to complete this follow-up, including those not in this study).

6) Study Endpoints

Our primary study endpoint remains to conclude if our current modality of whole-body cooling coupled with topiramate results in seizures or no seizures.

As well to determine the effect of adjuvant topiramate treatment on the outcome of newborns with perinatal depression (including neonatal encephalopathy) who are already receiving the therapeutic whole body cooling.

7) Informed Consent

One or both parents of the eligible infants are approached either

- (1) In person in the NICU at UCDMC by one of the investigators
- (2) By our Transport Nursing staff or Neonatal Fellow (if they are still at the outside referral center)

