The Pediatric Neurology service is by protocol consulted on all cooling patients. They will evaluate the infant and determine a neonatal encephalopathy score daily under the supervision of our Pediatric Neurologists. The presence of clinical seizures will be noted based on review of the bedside aEEG or cEEG. The aEEG/cEEG data will be reviewed in 3 hour increments and document the time when the voltages on the aEEG/cEEG first return to normal. The aEEG/cEEG is used throughout the cooling phase and is generally discontinued after rewarming is completed but may be continued longer for abnormal tracings such as seizures at the discretion of the Neonatology Attending. In addition, the Attending Pediatric Neurologist will assess quality of movements, posture, reflexes, and muscular tone, each infant's neurologic status will be categorized as normal (completely normal neurologic status), unspecific signs (eg, asymmetric muscle tone or reflexes) or abnormal with lack of reflexes and bilateral muscular hypotonia or hypertonia.

Additional tests in infants enrolled in this research study include: serum UCHL1 and urine levels of S100 β , both will be measured at enrollment, at the start of rewarming, and at one-week of life. Topiramate trough drug levels will be collected 24 hours after the first, third, and fifth doses. The drug levels will be run by the UCDMC laboratory. These

PROTOCOL TITLE: Topiramate for infants receiving whole body cooling in neonatal encephalopathy

are the only additional laboratory assessment that study infants will receive as a result of taking part in the study.

All infants on the cooling protocol, irrespective of the research study, will have an MRI with spectroscopy on day 5-7 of life. For this study, these images will be read by a single radiologist, our collaborator [name] of Neuroradiology. The reporting of MRI and MRS results will be standardized in conjunction with [name] to create a more consistent scoring method.

Following discharge, each infant will receive long-term developmental follow-up through the MIND clinic our High Risk Infant follow-up clinic. Infants will be seen at approximately 9, 18, and 27 months. The infants will have standardized Bayley Scale of Infant Development (BSID) III neurodevelopmental screening at these clinic follow-ups supervised by [name].

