The BSID-III contains 3 domains: cognitive, language (receptive and expressive communication), and motor (fine and gross motor). The cognitive scale includes items that assess sensory perceptual development, exploration and manipulation, object relatedness, concept formation, memory, and other aspects of cognitive processing. To allow comparison of results from the 3 domains, a composite score is calculated for each domain (mean, 100). A composite score below -2 SD (<70) is considered a severe delay for all domains. A Pediatrician will assess the quality of movements, posture, reflexes, and muscular tone at each clinic visit. Each infant's neurologic status will be categorized as normal gait and walking, unspecific neurological signs (eg, asymmetric muscle tone or reflexes, muscular hypotonia), or abnormal with upper and/or lower extremities muscular hypertonia (signs of cerebral palsy (CP) present).

9) Data and/or Specimen Management and Confidentiality

Power Calculation

Our primary hypothesis is that topiramate will reduce the frequency of early seizures (i.e. before hospital discharge). From our current data, 64% of infants have seizures prior to hospital discharge; a sample size of 42 will have an 80% chance of detecting a reduction of seizure rate by 2/3 with a p-value of 0.05.

Statistical Methods

Our primary outcome is that seizures before hospital discharge will be significantly reduced in the topiramate group compared to the controls. This will be assessed by nominal logistic regression with the presence or absence of seizures as the nominal dependent variable, and treatment group (topiramate or control) as an independent variable. Other independent variables will include those that are unbalanced between the treatment groups at randomization, and factors that could affect the risk of seizures (these would include neonatal encephalopathy score at study entry, time to initiation of cooling (< or \geq 3h), gender etc).

The effect of treatment assignment on neonatal encephalopathy score (measured daily) will be assessed by repeated measures ANOVA with neonatal encephalopathy score as the dependent variable, time and treatment assignment as the independent variable, and addition independent variables included as appropriate (see above). Time to normalization of aEEG/cEEG in the two different groups will be assessed by Kaplan-

PROTOCOL TITLE: Topiramate for infants receiving whole body cooling in neonatal encephalopathy

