Meier analysis. The effect of treatment on S100 β levels in the urine or UHCL1 in the blood and on other markers of tissue injury will be compared using ANOVA (for outcomes measured once) and by repeated measures ANOVA for those measured on more than one occasion, at predetermined times.

Effect of treatment assignment of development assessments will be assessed individually at the 9m, 18m and 27m examinations.

All tests will be considered significant at $p<0.05$. Where necessary, Tukey-Kramer's test will be used to account for multiple comparisons

Data Specimen/Management

Data specimens will be stored in the NICU and numerically coded, only those who are involved with this study will have access to the specimens. The specimens will only be stored for the duration of the study and thereafter discarded.

10) Data and/or Specimen Banking

There is no plan for specimen or tissue banking in the future.

11) Provisions to Monitor the Data to Ensure the Safety of Subjects

To monitor the safety of each newborn we will track the following variables closely during the intervention: blood gases, blood pressure (hypotensive episodes and required interventions), evidence of seizure activity, and serum topiramate levels. This study is only applicable to newborns with neonatal encephalopathy admitted to the NICU at UC Davis for cooling therapy. Neonatal encephalopathy is a life threatening disease with 30% chance of death and 64% chance of seizures during the neonatal period. These patients receive 24 hours daily continuous extremely close physiological and biochemical monitoring based on their underlying disease state.

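### Testing the Bayley scores separately at 9, 18 and 27 months leaves out a child's other scores when a visit is missed; one mixed model per domain would use them at little cost

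*Combined protocol and SAP*

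**What the plan says.** Section 2 makes development at 9, 18 and 27 months a secondary objective. Section 8 schedules the visits ("Infants will be seen at approximately 9, 18, and 27 months") and names the instrument: "The infants will have standardized Bayley Scale of Infant Development (BSID) III neurodevelopmental screening at these clinic follow-ups". Each of the three domains yields a composite with mean 100, and "A composite score below -2 SD (<70) is considered a severe delay for all domains", which implies an SD of 15.

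The whole analysis provision for these outcomes is one sentence in Section 9: "Effect of treatment assignment of development assessments will be assessed individually at the 9m, 18m and 27m examinations". It names no test and does not say what happens to a child who misses a visit.

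Other repeated outcomes are handled differently. The daily encephalopathy score "will be assessed by repeated measures ANOVA with neonatal encephalopathy score as the dependent variable", and tissue-injury markers are compared "by repeated measures ANOVA for those measured on more than one occasion, at predetermined times". Neither provision is extended to the Bayley scores. The plan's only mention of intention to treat, in Section 12, concerns a seizure between randomization and the first dose, not a missed clinic visit.

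**The concern.** A Bayley composite is age-standardised, so a child's scores at the three visits are on one scale and are likely to be correlated. When each visit is tested alone on those who attended, the 9- and 18-month scores of a child absent at 27 months play no part in the 27-month comparison. The same holds for any other missed visit.

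Two things are at stake. One is precision: the trial has 21 infants per arm before any death or missed visit, so each lost score widens the interval noticeably. The other is bias: if children with poor earlier scores are more likely to drop out in one arm than in the other, the attenders are no longer comparable, and a test on attenders alone cannot correct for it.

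**Working it through.** **The plan's own figure.** No sample size or power is given for the Bayley comparisons. The target of 42 was set for seizures, and this point does not depend on it. The usual two-sided formula without continuity correction, for 64% against 64%/3 = 21.3%, gives 20 per arm (40 in total), close to 42.

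**Inputs from the documents.** 21 per arm (Sections 5 and 8); SD (100 − 70)/2 = 15 (Section 8); mortality 30% (Section 11), though Section 2 says up to 30% and that hypothermia lowers it.

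**Assumptions.** The proportion m missing at 27 months and the between-visit correlation ρ are not in the documents. I take m from 10% to 35% and ρ from 0.3 to 0.8.

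**Step 1: precision of the separate test.** The detectable difference at 80% power, two-sided 0.05, is 2.80 × 15 × √(2/n).
- n = 21: 13.0 points.
- 20% missing, n = 21 × 0.8 = 16.8: 14.5 points.
- 30% mortality as well, n = 21 × 0.7 × 0.8 = 11.8: 17.3 points.

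**Step 2: gain from using the earlier scores.** With 9- and 18-month scores complete and equal correlations, the share of 27-month variance explained by the earlier two is R² = 2ρ²/(1 + ρ). The variance of a 27-month mean becomes (σ²/n_obs) × (1 − m·R²), so the proportion saved is m·R². R² is 0.138 at ρ = 0.3, 0.333 at 0.5, 0.576 at 0.7 and 0.711 at 0.8. This is a large-sample formula, so the table also gives simulated savings (15 per arm, SD 15, missing completely at random, maximum likelihood, 1,000 trials per setting).

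| Missing at 27 months | ρ = 0.3: formula / simulated | ρ = 0.5 | ρ = 0.7 | ρ = 0.8 |
|---|---|---|---|---|
| 10% | 1% / 0% | 3% / 2% | 6% / 7% | 7% / 10% |
| 20% | 3% / 2% | 7% / 4% | 12% / 11% | 14% / 15% |
| 35% | 5% / −1% | 12% / 7% | 20% / 19% | 25% / 24% |

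The two agree within simulation error, except at low correlation with high missingness. There, estimating the covariance in so few children uses up much or all of the gain.

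**Step 3: the gain in children and points.** At 20% missing from 21 per arm, effective n = 16.8/(1 − 0.2·R²). That is 17.3 at ρ = 0.3, 18.0 at 0.5 and 19.0 at 0.7, a recovery of 0.5 to 2.2 children per arm. The detectable difference falls from 14.5 to 14.3, 14.0 and 13.6 points. With 30% mortality as well, it falls from 17.3 to between 17.1 and 16.3. In the simulation at 20% missing and ρ = 0.5, the standard error moved only from 6.19 to 6.07 points.

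**Step 4: bias.** When dropout works alike in both arms, neither method shows visible bias. When it depends on the previous score in one arm only, the separate-visit estimate was off by 1.3 to 3.6 points and the mixed model by less than 0.7. In a deliberately extreme case, with low scorers leaving one arm and high scorers the other, the separate estimate was off by 4.3, 6.2 and 7.1 points at ρ = 0.5, 0.7 and 0.8; the mixed model stayed within 0.3. These are illustrations, not forecasts.

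**Step 5: test size.** With groups this small, a plain maximum-likelihood Wald test rejected a true null in about 5% to 10% of simulated trials (7% to 8% in most settings), against 4% to 7% for the t-test. The model therefore needs REML and a small-sample correction.

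**The case against.** The strongest reply is that this is a preference, not an error. Comparing an age-standardised score visit by visit is a legitimate analysis, the outcome is secondary, and no figure in the plan is wrong. The gain depends on two quantities that the documents do not give. Section 5 says that all cooled infants are asked to attend this follow-up, so attendance might be good, and at 10% missing the saving is at most about 10%. An unstructured model in 10 to 15 children per arm also inflates type I error unless it is corrected. All of this stands. It limits the size of the point and adds a condition to the fix, but it does not make the separate tests preferable.

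Three stronger readings are tempting and are not supported:
- A reader might infer that the separate tests are invalid or already biased. They are valid under missing completely at random, and nothing in the documents shows that dropout would differ by arm.
- A reader might treat 27 months as the decisive visit, or as the one known to lose most children. The protocol ranks no visit and gives no attrition by visit. The only one it singles out is 18 months, for a neurological examination (Sections 13 and 14). I use 27 months above because it is the last visit.
- A reader might turn the upper corner of the table into a headline gain in sample size. That corner needs both high attrition and high correlation, and neither is documented.

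Death could also remove more children than missed visits. At the quoted 30%, 21 per arm becomes 21 × 0.7 = 14.7. Since all enrolled infants are cooled, that is a pessimistic figure, and a mixed model does not resolve deaths in any case.

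**Conclusion.** The point holds in limited form, as a cheap improvement. Under the plan as written, a child who misses a visit contributes nothing to that visit's Bayley comparison even when other scores exist. A likelihood-based model would recover some of that information and would protect against dropout that depends on observed scores differently by arm. For the 27-month difference, with 10% to 35% missing, the variance saved is about nothing at correlation 0.3, roughly 2% to 12% at 0.5 and roughly 7% to 25% at 0.8. These figures rest on the assumed attrition and correlation, SD 15, similar correlation between all pairs of visits and earlier visits attended. The bias protection rests on missing at random. If attendance is nearly complete, little changes.

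**What to change.** In Section 9, replace the provision for separate assessment with the following, for each Bayley domain:
- one linear mixed model among surviving children, with arm, visit and arm-by-visit terms, including every attended visit;
- unstructured covariance across visits, fitted by REML, with a Kenward-Roger or similar small-sample correction;
- the arm difference with its interval at each of 9, 18 and 27 months, with no visit ranked first unless the sponsor names one in advance.

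Extending the plan's repeated measures ANOVA would not serve, because in its classical form it usually drops any child with a missing visit.

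Report deaths by arm separately, and state how a death after a scored visit is treated, since the model would otherwise handle it like a missed visit. The categorical neurologic status from the follow-up clinic also needs its own analysis.

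The cost is a change of analysis wording, a slightly more complex analysis and reliance on missing at random. No extra data are needed. All three per-visit comparisons are kept, and with complete attendance the point estimates equal those of the separate analyses.

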Babies will be ineligible if they have major congenital abnormalities. If the baby had a proven (i.e. electrically confirmed seizure) prior to enrollment they would not be eligible for the study. If a seizure occurred after enrollment/ randomization but before the first dose of study medication the protocol would continue based on the intention to treat. Treatment of seizures will be guided by our Pediatric Neurologists (who will be unaware of treatment assignment). Currently we do not use topiramate for treatment of seizures, and do not intend to change our management of seizures in the foreseeable future. Our first line treatment is phenobarbital, second line is levetiracetam, and the third line treatment is ativan. So, any baby who developed seizures during the protocol would receive our current standard of care, but continue to be in the study. The study protocol will not change the management of seizures should they occur. Once enrolled, a baby would not be withdrawn because of seizures (irrespective of number). We would manage these seizures according to our current clinical practice (see above). Although our primary endpoint (seizures) has been met, we would continue to collect data on secondary endpoints and on safety measures. Patients with renal deficiency (creatinine >2 mg/dL) and liver failure (ammonia >100 mcmol/L) will not be eligible for the study.

13) Risks to Subjects

Newborns with neonatal encephalopathy are very vulnerable. Given the high risk of lifelong neurologic injury and the low risk of the proposed intervention, the risk to benefit ratio of this study is reasonable. Every effort will be made to ensure that the infants receive excellent care and that the parents of the infants fully understand the benefit/risk of the study. Topiramate has been extensively used to treat variety of neurological diseases including seizures in adults, children, and infants. It is a widely used drug with minimal side effects. In adults, topiramate can cause side effects not likely to be obvious in neonates (e.g. paresthesias, dizziness, fatigue, drowsiness, depression, coordination problems, nausea, and difficulty concentrating). These should not be a problem in study infants as babies who receive whole body cooling are routinely sedated with morphine, and any additional sedative effect from topiramate is likely to be minor. Babies who receive whole body cooling are NPO so the possible side effect of nausea by topiramate should be minimized.

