PROTOCOL TITLE: Topiramate for infants receiving whole body cooling in neonatal encephalopathy

Pharmacological, pharmacokinetic, and therapeutic studies of chronic administration of topiramate have been conducted to determine its effective dose and to demonstrate its safety in newborn infants (2,4,5). We propose the use of the minimum therapeutic dose of 5 mg/kg/day topiramate for 5 days. However even side effects associated with long term (months) administration of topiramate to infants appear to be minimal. In this study, the serum level of the drug will be monitored in addition to arterial blood gases, blood pressure, and clinical evidence of seizure for any possible side effects. Several studies have used topiramate for treatment of epilepsy or neonatal encephalopathy in infants. In a recent large double-blind placebo controlled prospective study of different doses of topiramate as an adjunctive therapy to conventional antiepileptic drugs in infants a 10% increased rate of fever, diarrhea, vomiting, weight decrease, and viral infection was reported (15). These side effects were dose related and occurred only in infants treated with a higher dose (25 mg/kg/day) of topiramate.

Adverse effects of topiramate administration in this age and population of infants that are not published but have been reported to FDA include: viral infection, bronchitis, pharyngitis, rhinitis, otitis media, upper respiratory infection, cough, and bronchospasm. An increased risk for infections (any topiramate dose 12%, placebo 0%). Topiramate resulted in an increased incidence of patients with increased creatinine (any topiramate dose 5%, placebo 0%), BUN (any topiramate dose 3%, placebo 0%), and an increased incidence of decreased potassium (any topiramate dose 7%, placebo 0%). Monitoring of creatinine, BUN, potassium, and urine output is the standard of care in all patients with neonatal encephalopathy. The risk of viral infections is unlikely given the short duration of therapy. Many infants receiving whole body cooling may require mechanical ventilation due to their underlying disease so bronchospasm is unlikely, and easily treatable should it occur.

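### Section 11 has the study team track each infant's serum topiramate level, which can show the arm, and no passage keeps the results from investigators, the neonatology attending or the EEG reviewers

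*Combined protocol and SAP*

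**What the plan says.** Section 8 (Procedures Involved) describes a randomized, double-blind, placebo-controlled trial. The same section sets the sampling: "Topiramate trough drug levels will be collected 24 hours after the first, third, and fifth doses". On the assay it adds: "The drug levels will be run by the UCDMC laboratory".

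Section 11 (Provisions to Monitor the Data to Ensure the Safety of Subjects) gives the results a use during treatment: "To monitor the safety of each newborn we will track the following variables", and the sentence continues "closely during the intervention: blood gases, blood pressure (hypotensive episodes and required interventions), evidence of seizure activity, and serum topiramate levels". Section 13 (Risks to Subjects) repeats it: "the serum level of the drug will be monitored in addition to arterial blood gases, blood pressure, and clinical evidence of seizure".

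Controls receive placebo (Section 8). On seizure management, Section 12 (Withdrawal of Subjects) says "Currently we do not use topiramate for treatment of seizures" and lists other drugs.

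The plan has four provisions on blinding or access:

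- Section 8: pharmacy makes the two solutions alike in look and volume.
- Section 9: specimens carry numeric codes, and only people working on the study may handle them.
- Section 11: the DSMC is blinded and sees arms labelled A and B. Drug levels are not among the data it is listed to receive.
- Section 12: the pediatric neurologists who guide seizure treatment will not know the assignment.

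**The concern.** A topiramate level is close to a direct readout of the arm. The documents name no source of topiramate other than the study drug, so a measurable level points to the active arm. Section 11 asks the study team, in the first person plural and without naming a role, to follow these levels while treatment is under way. Someone must therefore see them then, and the plan does not say who.

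The outcome at stake is the primary one. The Section 9 hypothesis is that "topiramate will reduce the frequency of early seizures (i.e. before hospital discharge"), and Section 8 has seizures noted from the bedside aEEG or cEEG. Section 8 also leaves the length of recording partly open: it "may be continued longer for abnormal tracings such as seizures at the discretion of the Neonatology Attending". A person who knows the arm could read a doubtful tracing differently, score encephalopathy differently, or decide differently whether to keep recording an infant with an abnormal but seizure-free tracing. Time to EEG normalization and the daily encephalopathy score, both analysed under Section 9, are exposed in the same way. That these readings involve judgement is my view; the documents do not discuss it.

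**Working it through.** The plan gives no figure on this point, so there is none to reproduce; the sample-size calculation does not enter. There are two checks: who is covered by a blinding provision, and when a result could arrive.

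**Coverage.**

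- Neurologists: intent stated (Section 12), no procedure for assay results.
- DSMC: intent and A/B codes stated (Section 11), no procedure for assay results.
- Investigators: no provision for level results.
- Neonatology attending, who decides on longer EEG: no provision.
- EEG reviewers: not named in Section 8, no provision. If they are the neurologists, the Section 12 intent applies.
- Laboratory: runs the assays, with no statement of how or to whom it reports.

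The Section 9 coding and access rule covers specimens. It does not cover results, and coding hides nothing from a team that holds the key.

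**Timing.** Inputs from Section 8: 72 h of cooling, 12 h of rewarming, EEG until rewarming is complete, five daily doses, and draws 24 h after doses 1, 3 and 5. Let hour 0 be the start of cooling, d the hour of dose 1 and t the laboratory turnaround, with doses exactly 24 h apart.

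- Scheduled EEG: 72 + 12 = 84 h.
- Draws: d + 24; (d + 48) + 24 = d + 72; (d + 96) + 24 = d + 120.
- Scheduled EEG left when the first result returns: 84 − (d + 24) − t = 60 − d − t. This is positive only if t < 60 − d.
- Second result: 84 − (d + 72) − t = 12 − d − t, positive only if d + t < 12 h.
- Third result: 84 − (d + 120) − t = −36 − d − t, never positive. It can matter for EEG only if recording is extended.

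The documents give neither d nor t. I assume d from 0 to 48 h, because consent is sought after cooling starts (Section 8), infants over one day old are excluded (Section 4) and dose 1 falls on the day of enrollment (Section 8). The top of that range is an outer limit. The values of t are also assumed.

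| d (h) | t must be under (h) | EEG left, t = 24 h | EEG left, t = 48 h |
|---|---|---|---|
| 0 | 60 | 36 | 12 |
| 12 | 48 | 24 | 0 |
| 24 | 36 | 12 | −12 |
| 36 | 24 | 0 | −24 |
| 48 | 12 | −12 | −36 |

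Negative values mean that the result comes after scheduled EEG has ended. With an early first dose and a quick assay, the first result arrives with a day or more of scheduled recording to go. With a late dose or a slow assay it arrives too late to affect scheduled recording.

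**The case against.** The strongest reply is that measuring drug levels and keeping a blind are compatible, and that no passage says an investigator, attending or neurologist sees a result. A laboratory or pharmacy instruction outside these documents may already handle it. That is fair, and it limits the claim to what the protocol permits. It does not remove the point, because Section 11 assigns real-time tracking to the study team with no rule protecting the blind.

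Several stronger readings are tempting, and the documents do not support them:

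- *The blind has been broken.* Nothing shows this.
- *Only the topiramate arm is sampled.* Section 8 lists the levels among the tests for all enrolled infants, and Section 11 speaks of each newborn. Both imply sampling in both arms.
- *The neurologists are unprotected.* Section 12 commits to keeping them blind, and showing them a level would breach that. Only the mechanism is missing.
- *Any discretionary extension of EEG can bias the primary outcome.* An infant recorded longer because of seizures has already met the endpoint, as Section 12 recognizes. Only extension for other abnormal tracings could change whether a seizure is found.
- *The exposure lasts days, because the outcome runs to discharge.* If the third draw precedes discharge, the outcome window stays open at least (d + 120) − (d + 24) = 96 h after the first draw. That is not time under EEG, which generally stops after rewarming. Even with instant turnaround, scheduled EEG after the first draw is at most 60 h.
- *The 13 infants already enrolled (13/42 = 31% of the target) measure the damage.* That share measures neither exposure nor bias.

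**Conclusion.** The point holds as a gap between a stated tracking rule and a stated blind. Followed as written, Sections 8, 11 and 13 can show the arm to people who note seizures on EEG, score encephalopathy or decide on longer recording for non-seizure abnormalities. The plan's blinding provisions do not reach assay results. The inference rests on two things in the documents: controls receive no study topiramate, and the site does not use it for seizures.

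The size of any bias is unknown. The only bound is on timing: a first result within scheduled EEG needs turnaround under 60 − d hours, and both quantities are missing from the documents. This is worth fixing because the protection is cheap, not because the results are shown to be compromised.

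**What to change.** Amend Sections 8, 11 and 13 to say the following:

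1. Coded level samples from both arms, as the text already implies, are reported only to a designated unblinded person. Existing pharmacy staff are an option, since pharmacy already randomizes. That person should not sit on the DSMC, which must stay blinded and lists a clinical pharmacist among its members.
2. That person does the safety tracking of levels, so the tracking is moved and not removed.
3. Results are not visible to investigators, treating staff, neurologists or EEG reviewers until database lock, except through a stated safety-unblinding route consistent with the DSMC's powers in Section 11.
4. For the 13 infants already enrolled (Section 5), record whether level results were visible to the team, so that readers can judge the blind.

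No level threshold or clinical action is proposed here. The cost is protocol wording and a laboratory routing instruction. The downside is that the treating team does not routinely see levels in real time.
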